## Research Strategy

### Recruitment and Retention.

Clinicians working on the rehabilitation units will inform TBI patients of the study. If the patient is interested, the site-PI will discuss the study and obtain informed consent, which will include their permission for

the caregiver to participate. The site-PI will then invite the caregiver to participate and obtain informed consent. We selected a 12-month enrollment period because, based on TBI admissions data and previous studies conducted at the 3 sites, this window is necessary to enroll 110 dyads. Dyads will be randomly assigned to the treatment or control group, and each patient and caregiver will be paid the local currency equivalent of \$10 per data collection. Demographic and baseline data will be collected prior to discharge, as well as outcome data at 2 and 4 months post-discharge (Figure 2). A 4-month follow-up period was selected instead of a longer follow up because our research has suggested that the inpatient stay on an acute unit and the first 3 months post-discharge are the most stressful time periods for family TBI caregivers, and that their mental health and health related quality of life only increase marginally between 3 months and 1 year post-discharge. Therefore, the first several months after discharge are a critical time frame for intervention and follow up, as these variables remain fairly constant after initiating a particular trajectory.

**TBI Patient Inclusion Criteria.** All patients treated for TBI and discharged home will be invited to participate if they meet the following criteria: (1) give permission for their caregiver to participate; (2) sign an informed consent giving permission to obtain demographic and health information; (3) have the ability to communicate over the phone for data collection; and (4) are between 18-60 years of age. If a patient is aphasic (estimated 10%), arrangements will be made to collect data with self-administered paper-pencil reports via postal mail.

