*Data Collection 1.* After enrollment and immediately before discharge (as well as before Session 1 for the treatment group), demographic and baseline data will be collected from the TBI patient and caregiver. The site-PI will meet with the patient and caregiver separately. The site-PI will read items aloud from an assessment packet to the patient and caregiver, circling participants’ responses. The caregiver packet will include validated measures of caregivers’ health status, health care utilization/cost, burden, depression, sense of coherence, quality of informal care provided, and relationship satisfaction. The patient packet will include validated measures of patients’ functional and health status, health care utilization/cost, self-perceived burden, depression, quality of informal care received, and relationship satisfaction.

*Data Collection 2-3.* At 2 and 4 months after hospital discharge, the site-PI will collect follow-up data from the TBI patient and caregiver over the phone using the same validated measures and in the same format as during Data Collection 1. For the treatment group only in Data Collection 2, the site-PI will also collect qualitative information from the

*Outcome Measures.* The majority of outcome measures have previously been translated and validated among Spanish speakers. For the four that have not (Exemplary Care Scale, Relationship Assessment Survey, Self-Perceived Burden Scale, and Brief Health Literacy Screening Tool), we will use Chapman and Carter’s methodology to translate and back-translate the measures, whereby a bilingual and bicultural researcher will translate the original measure into Spanish, and a separate bilingual and bicultural researcher blinded to the NCT00207803

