original measure will then back-translate it into English. Any discrepancies between the original English and back-translated English will be resolved mutually. We will pilot the four translated measures with rehabilitation teams at each site and amend the instruments to improve their face validity in the three local cultures while ensuring the standardization of each instrument across the three sites. We will then administer the instruments over the course of our study, and after collecting outcome data, we will run exploratory factor analyses to establish each measure's factor structure, as we have done and advocated for in our own research investigating measure psychometrics among individuals after acute TBI and across various global regions. Based on these analyses, we will remove items that do not accurately measure the constructs under scrutiny.

*Functional Independence Measure (FIM; patient functional status).* The FIM is the most widely used method of assessing function and assistance needs in individuals with a disability. The FIM has a total score and six subscales: self-care, sphincter control, transfer capability, locomotion, communication, and social cognition. The FIM consists of 18 items, and responses use a 7-point ordinal scale. The reliability of the FIM is well established: in a meta-analysis the median inter-rater reliability for the total FIM was 0.95 and the median test-retest and equivalence reliability values of 0.95 and .92 respectively.

*Exemplary Care Scale (ECS; patient and caregiver rating of quality of informal care).* The ECS is an 11-item self-report questionnaire that assesses the extent to which caregivers engage or do not engage in activities that help care recipients maintain dignity and respect. Response choices are on a Likert scale (1 = never; 2 = sometimes; 3 = often; 4 = always), and higher scores indicate higher exemplary care. Parallel caregiver and care recipient versions are available, with equivalent measurement properties. The ECS has been shown to be a valid measure of the quality of informal care for individuals with disabilities.

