A Culturally Sensitive Intervention for TBI Caregivers in Latin America

PI: [name]

NCT #: 02207803

Virginia Commonwealth University Internal Review Board (IRB): HM20001660

Document approval date: 5/6/2014

Document Type: SAP

What is the TAP's impact on Latino caregivers' health status, burden, depression, sense of coherence, quality of informal care provided, and relationship satisfaction?

Analytic Plan: A Greenhouse-Geisser-adjusted repeated measures multivariate analysis of variance (RMANOVA) with one fixed effect of treatment group (TAP vs. control), the repeated measures over time (baseline, and 2 and 4 months after discharge), and the treatment group by time interaction will be conducted for the set of dependent variables in Q1. If an omnibus effect is found, follow-up Bonferroni-corrected ANOVAs will identify specific locations of effects. These dependent variables rarely correlate with each other higher than .60,⁶¹ so do not reach the .70 level that Tabachnik and Fidell⁶² identify as problematic.

What is the TAP's impact on Latino TBI patients' functional and health status, self-perceived burden, depression, perceptions of quality of informal care received, and relationship satisfaction?

Analytic Plan: The same analyses will be used for the patient dependent variables.

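### Minor, cheap improvement: ECS, RAS and SPBS scoring stays open until follow-up data exist; fix the item sets from arm-masked baseline responses and lock them before any comparison by arm

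*Protocol*

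**What the plan says.** The protocol's Outcome Measures section singles out the instruments not yet validated in Spanish: "For the four that have not (Exemplary Care Scale, Relationship Assessment Survey, Self-Perceived Burden Scale, and Brief Health Literacy Screening Tool". These are translated, back-translated and piloted, and the team may "amend the instruments to improve their face validity in the three local cultures". They are then given throughout the study. Next, "after collecting outcome data, we will run exploratory factor analyses to establish each" measure's factor structure, and on that basis "we will remove items that do not accurately measure the constructs under scrutiny". Earlier work is cited for the approach.

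Recruitment and Retention separates the baseline from the outcome data: "Demographic and baseline data will be collected prior to discharge, as well as outcome data at 2 and 4 months post-discharge". Data Collection 2-3 has follow-up collected "using the same validated measures and in the same format as during Data Collection 1", so item responses exist at all three time points.

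The SAP uses these constructs as dependent variables in a repeated measures MANOVA (RMANOVA) for caregivers and another for patients. For each: "If an omnibus effect is found, follow-up Bonferroni-corrected ANOVAs will identify specific locations of effects". It does not mention factor analysis, item removal or scoring.

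**The concern.** Dropping items changes the outcome variable itself. Here that step is dated after the 2- and 4-month data, and the removal criterion is given in words only. Two things could follow.

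- If follow-up responses enter the factor analysis, they carry any effect of the Transition Assistance Program (TAP). Treatment could then affect which items are kept, and so the effect that is reported.
- Without a written rule and a lock, nothing on paper prevents items being chosen with arm results in view.

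The scoring of the other outcome scales, such as the Zarit Burden Interview and the PHQ-9, is untouched. Their follow-up ANOVAs, however, depend on an omnibus test that includes the affected scales.

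**Working it through.** **1. Timing.** The factor analyses come after outcome data are collected, and the protocol uses that term for the data obtained "as well as outcome data at 2 and 4 months post-discharge", after randomisation. This dates the analysis. It does not say which responses enter it.

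**2. Scope.** The SAP's caregiver question lists six constructs, of which two use these scales (informal care, ECS; relationship satisfaction, RAS). The patient question also has six once functional and health status are counted separately, of which three are affected (SPBS, ECS, RAS). The fourth translated tool, the literacy screen, is not an SAP outcome. These are counts of constructs; the SAP does not say whether SF-36 dimensions or FIM subscales enter separately.

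**3. Inputs.** From the protocol: 11 ECS, 7 RAS and 10 SPBS items; 110 dyads enrolled; 84 expected complete, so 42 per arm. (110 × 0.75 = 82.5; the stated 84 implies 1 − 84/110 = 23.6% attrition, a difference that does not matter here.) Assumed, because the documents give none: one factor per scale, equal loadings of 0.5, 0.6 or 0.7, a 0.40 loading cut-off, 5% significance, one score per construct, correlation 0.4 between outcomes and 0.6 over time, normal complete data.

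**4. Fixed rule, arm-blind, no treatment effect.** In simulation (10,000 runs per setting; omnibus test on 6 × 2 = 12 group-by-time contrasts; follow-up ANOVAs at 0.05/6), items below 0.40 at follow-up were removed without regard to arm. The omnibus false-positive rate was 4.6–5.3%. The two-stage rate (omnibus plus at least one follow-up ANOVA) was 1.5–2.0%. There is no inflation.

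**5. Can treatment influence which items are kept?** Take loading 0.5, so items correlate 0.5² = 0.25 within arm, and let TAP shift an item by 0.5 SD. With equal arms pooled, a shifted item's variance becomes 1 + 0.5²/4 = 1.0625, and the covariance of two shifted items becomes 0.25 + 0.0625 = 0.3125.

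- *All items but one move.* Two moved items correlate 0.3125/1.0625 = 0.294, so they load √0.294 = 0.542. The unmoved item correlates 0.25/√1.0625 = 0.243 with them and loads 0.243/0.542, about 0.45. It has slipped towards the cut-off.
- *Only one item moves.* It correlates 0.243 with the others, which still load 0.5, so it loads 0.243/0.5 = 0.485. Now the moved item slips.

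Simulated consequences at n = 84:

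| Pattern | Loading 0.5 | Loading 0.6 |
|---|---|---|
| All but one move: deletion of the unmoved item | 16–19% with no effect, 31–34% with effect | 1.2–2.2% with no effect, 4.7–5.2% with effect |
| Same: average change in mean-item effect | +2.8 to +4.3% | +0.4 to +0.8% |
| Same: average change in standardised effect | +1.3 to +1.9% | at most +0.6% |
| Only one moves: deletion of the moved item | 16–19% with no effect, 20–23% with effect | – |
| Same: average change in mean-item effect | −3 to −7% | about −1% |
| Same: change in standardised effect | down to about −11% | about −1% |

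At loading 0.7 there is essentially no change. In runs where exactly the unmoved item is deleted, the mean-item effect is larger by a factor of p/(p − 1): 11/10, 7/6 or 10/9 (10%, 17%, 11%). Those figures are conditional on the deletion. The averages in the table describe the expected distortion.

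**6. Worst case: scoring steered by arm results.** Allow the full scale or dropping one or two of each scale's three weakest items: 1 + 3 + 3 = 7 scorings per scale, 7² = 49 combinations for caregivers and 7³ = 343 for patients. The omnibus rate rises from 5% to 8.1–9.4% (caregivers) and 9.2–11.5% (patients). The two-stage rate rises to 2.6–3.2% and 2.8–3.8%.

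**7. Baseline-only alternative.** With 110 dyads and no treatment effect in the factor-analysed responses, the average overstatement in the all-but-one pattern is at most 0.1%. Chance deletion of at least one valid item remains: 63–71% at loading 0.5, about 6% at 0.6, none at 0.7.

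**The case against.** The stated criterion is psychometric. Nothing in the documents suggests that items would be chosen by arm or by result, and a fixed arm-blind rule leaves the error rates intact. That stands. A reader might infer that the plan inflates type I error; the documents do not support this. The omnibus rates of roughly 8–11.5% need a departure from the stated criterion, and even then the two-stage rate, which governs claims about specific outcomes, stays below 5%.

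A reader might also infer that trimming would exaggerate the benefit of TAP. That follows only if TAP moves most items. If it moves few, the distortion is downward, and the documents do not say which pattern to expect. A shift of 0.5 SD per item is also generous: at loading 0.5 with all items but one moved it is a scale-level effect of 5/√38.5 = 0.81 for the ECS and 3/√17.5 = 0.72 for the RAS. The protocol reports medium effects in its pilot (for strain and depression), though it expects larger ones here. With a scale-level effect of 0.5 the mean-item overstatement falls to 1.2–2.4%, and the standardised effect is slightly attenuated (0.5–0.7%).

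An operational rule may sit in the cited work, so its absence from the protocol and SAP does not show that none exists. The wave is not stated either. Finally, these scales lack Spanish validation, so there is good reason to examine their items.

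What survives is narrower: the protocol states a procedure whose timing leaves outcome scoring open after randomised follow-up, and data already planned allow a cleaner one. Masking cannot simply be assumed. At Data Collection 2 the site-PI gathers qualitative information from the treatment group only, so at least one role knows the arm, and the documents do not say who runs the factor analyses.

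**Conclusion.** The point holds as a minor, cheap improvement. Scoring for 2 of 6 caregiver and 3 of 6 patient constructs is left open until follow-up data from randomised dyads exist, with no stated wave, cut-off, arm-blind step or lock. The exposure is undefined discretion plus a small distortion of unknown sign if follow-up responses are used; it is not demonstrated bias. At loading 0.5 the distortion is a few percent in most patterns, with extremes of about 7% (mean-item) and about 11% (standardised, only one item moving). At loading 0.6 it is about 1% or less. Every size given here rests on the assumed loadings and the 0.40 cut-off.

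**What to change.** In the protocol and SAP:

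- Run the factor analyses on Data Collection 1 responses only, which precede Session 1, pooled over arms with arm labels removed.
- Write the factor-retention and loading rule beforehand; if the cited work contains one, state it.
- Lock one item set per scale and rater (caregiver and patient versions separately), used at all three time points, before any comparison by arm.
- Report the RMANOVA with the full as-administered scores, after the pilot amendments, alongside.

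The cost is one or two sentences and one extra analysis. No new data are needed, because the same measures are given at Data Collection 1. There are two downsides: a baseline-only rule can still delete valid items by chance, and it may miss items that work poorly only after discharge. Making the full scores the main outcomes would avoid chance deletion, but it could keep faulty translated items in the main analysis, so that choice is more of a trade-off.

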A Culturally Sensitive Intervention for TBI Caregivers in Latin America

PI: [name]

NCT #: 02207803

Virginia Commonwealth University Internal Review Board (IRB): HM20001660

Document approval date: 5/6/2014

Document Type: SAP

What is the TAP's impact on Latino caregivers' health status, burden, depression, sense of coherence, quality of informal care provided, and relationship satisfaction?

Analytic Plan: A Greenhouse-Geisser-adjusted repeated measures multivariate analysis of variance (RMANOVA) with one fixed effect of treatment group (TAP vs. control), the repeated measures over time (baseline, and 2 and 4 months after discharge), and the treatment group by time interaction will be conducted for the set of dependent variables in Q1. If an omnibus effect is found, follow-up Bonferroni-corrected ANOVAs will identify specific locations of effects. These dependent variables rarely correlate with each other higher than .60,⁶¹ so do not reach the .70 level that Tabachnik and Fidell⁶² identify as problematic.

What is the TAP's impact on Latino TBI patients' functional and health status, self-perceived burden, depression, perceptions of quality of informal care received, and relationship satisfaction?

Analytic Plan: The same analyses will be used for the patient dependent variables.

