**Caregiver Inclusion Criteria.** TBI caregivers are eligible to participate who meet the following criteria: (1) have a telephone in the home or cellular phone and are able to talk on the phone; (2) sign an informed consent; (3) score at least a 13 on a health literacy screening tool; and (4) are between 18-85 years of age. Caregivers with scores below 13 will identify a family member or friend to review the guidebook with the caregiver. If no one is identified, the TAP clinician will review the materials with the caregiver.

**Sample Estimation and Power.** We anticipate that during a 12-month enrollment period, we will enroll approximately 110 caregiver-patient dyads ( $n = 220$ ), of which 55 will be in the treatment group and 55 will be in the control group. Of the 110 dyads, 20 will be in Cali, Colombia; 20 in Neiva, Colombia; and 70 in Mexico City, Mexico. Allowing for a 25% attrition rate based on our previous data collection with the TAP, over the 4-month data collection period, we estimate complete data on 84 dyads.

In order to determine the effect size that a final  $n$  of 84 dyads would be able to uncover, we performed a power analysis using G\*Power 3 software for a repeated measures multivariate analysis of variance (RMANOVA) with three time points and two groups. This RMANOVA would uncover all large and medium-size effects, as well as many small-size effects. Our prior pilot study on the TAP generally showed medium-size effects on caregiver strain and depression, so our estimated sample size should be sufficient. Additionally, in the proposed study, the intervention will include in-home interventions of 60-minute duration, as opposed to the 30-minute duration in our previous pilot study. We are therefore expecting a larger effect size in the proposed study. If the TAP is found to be effective based on these analyses, at the end of the study, caregivers in the control group will receive the caregiving guidebook that had been provided to the intervention group as well as a written summary of the problem solving techniques and skills addressed in the intervention.

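### As written, the RMANOVA uses complete records only and does not adjust for baseline, so the test that gates all outcomes forgoes precision that the collected data could give

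*SAP*

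**What the plan says.** The SAP's Analytic Plan names one method, "A Greenhouse-Geisser-adjusted repeated measures multivariate analysis of variance (RMANOVA"), with a group effect, three time points (baseline, 2 and 4 months) and their interaction. It "will be conducted for the set of dependent variables in Q1", that is, for health status, burden, depression, sense of coherence, quality of care given and relationship satisfaction taken together. The outcomes are then gated: "If an omnibus effect is found, follow-up Bonferroni-corrected ANOVAs will identify specific locations of effects". For the six patient constructs, "The same analyses will be used for the patient dependent variables".

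On loss to follow-up, the protocol's Sample Estimation and Power paragraph reads "Allowing for a 25% attrition rate based on our previous data collection" and then "over the 4-month data collection period, we estimate complete data on 84 dyads", out of 110 enrolled. Its power statement rests on those 84. Neither document mentions imputation, a mixed model, an analysis set or any other rule for missing scores.

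**The concern.** A classical multivariate RMANOVA needs a full row: every outcome at every time point. Without prior imputation, a person who misses one visit leaves the omnibus test entirely, and the baseline and any follow-up scores already given go unused. Exclusion is per person within each model, so a missing patient score does not remove the caregiver.

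A second feature costs more. Because baseline is one of the repeated measures, the group-by-time test compares changes from baseline and does not use baseline as a covariate. In a randomised trial the covariate form is more precise whenever the correlation between visits is below 1.

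At stake is the gate. If the omnibus test misses, no outcome is tested, so lost precision there affects the whole trial.

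**Working it through.** **The plan's own figure.** 110 × (1 − 0.25) = 82.5, against 84 stated. The two agree to within two dyads (84/110 implies 23.6% attrition). Between 26 and 28 dyads are therefore expected to be incomplete.

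**Inputs.** From the protocol: 55 per arm and 25% attrition. Assumed, because the documents do not give them: outcome SD 1, equal correlation ρ between visits of 0.5 or 0.7, permanent dropout equal in both arms, and 55 × 0.75 = 41.25 completers per arm. The target is the group difference averaged over 2 and 4 months.

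**Step 1, planned change contrast, completers.** SE = √[(1.5 − 1.5ρ) × 2/41.25].
- ρ = 0.5: √(0.75 × 2/41.25) = 0.191
- ρ = 0.7: √(0.45 × 2/41.25) = 0.148

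**Step 2, same completers, baseline as covariate.** SE = √[((1 + ρ)/2 − ρ²) × 2/41.25].
- ρ = 0.5: √(0.50 × 2/41.25) = 0.156, a cut of 18%
- ρ = 0.7: √(0.36 × 2/41.25) = 0.132, a cut of 11%

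**Step 3, also keep people with a 2-month but no 4-month score.** Let n₂ be the number per arm seen at 2 months. Given baseline, each visit has variance s = 1 − ρ², and the covariance between visits is c = ρ − ρ²; let b = c/s. Then SE² = ((1 + b)/2)² × s × 2/n₂ + ¼ × (s − c²/s) × 2/41.25.

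| Dropout timing | n₂ | SE, ρ = 0.5 | SE, ρ = 0.7 | Further cut |
|---|---|---|---|---|
| All before month 2 | 41.25 | 0.156 | 0.132 | 0% |
| Split evenly | 55 × √0.75 = 47.6 | 0.149 | 0.126 | about 5% |
| All after month 2 | 55 | 0.142 | 0.120 | about 9% |

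These formulas treat the covariance as known. Simulation with estimated covariance and the even split gave 0.157 falling to 0.150 (ρ = 0.5) and 0.133 falling to 0.126 (ρ = 0.7). That is worth about 8 to 9 extra completers: (0.1571/0.1499)² × 82.5 = 90.6 and (0.1328/0.1263)² × 82.5 = 91.2.

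**Step 4, the gate (indicative only).** The protocol says "Our prior pilot study on the TAP generally showed medium-size effects on caregiver strain and depression", so the scenario puts 0.5 SD on two of six outcomes at both follow-ups, with correlation between outcomes of 0.3 to 0.5 and even dropout. For an unadjusted 12-df group-by-time test (noncentral F, 12 and 69.5 df), noncentrality runs from 14.9 to 19.6 in completers and from 17.5 to 23.0 with all observed scores at ρ = 0.5. Power is then 64–79% against 73–86%. At ρ = 0.7 it is 89–97% against 94–99%. Neither side adjusts for baseline.

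**The case against.** **The loss is already budgeted.** This stands. The protocol sizes the trial on 84 completers, so a reader who infers that planned power is overstated by this loss would be wrong. What is lost is extra precision.

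**Most of the gain is baseline adjustment, not retained cases.** This also stands, and Steps 2 and 3 keep the two apart. If everyone who drops out leaves before month 2, retaining incomplete cases adds nothing to the baseline-adjusted model.

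**The 12-df test may not be the one the SAP names.** A Greenhouse-Geisser correction belongs to the averaged, univariate-type test. Simulating that version with 41 per arm, compound symmetry and no reduction in df gave completers' power of 69–84% (ρ = 0.5) and 93–98% (ρ = 0.7), somewhat above Step 4. The version using all observed scores would rise too, so a gap may remain, but Step 4 cannot be read as the power of the named test.

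**Bias.** A reader might infer that a completers' comparison is biased. The documents do not show this: they give one overall attrition figure, no pattern by arm, and the same payment per data collection in both arms. In simulation the completers' contrast was unbiased when dropout was random or followed the same pattern and rates in both arms. False-positive rates stayed at 4.4–6.1% even when dropout followed the last observed score differently by arm.

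**Scattered missing items.** A reader might also expect many further losses from single missing items. That is unlikely, because "The site-PI will read items aloud from an assessment packet to the patient and caregiver" and circles the answers. The exception is aphasic patients on postal forms, about 11 of 110 at the protocol's 10% estimate.

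**Conclusion.** The point holds, as one about precision. Followed as written, the plan drops partial records from the gating test and forgoes baseline adjustment. Under the stated assumptions, baseline adjustment would cut the standard error by 11–18%, and keeping incomplete cases by a further 0–9%. The size depends on visit correlations and dropout timing that the documents do not give, so confidence is medium. The documents do not support a claim of overstated power or of demonstrated bias. Because the remedy is cheap and the affected test controls every outcome, the change should be made.

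**What to change.** For each outcome, make the primary analysis a likelihood-based mixed model for repeated measures with baseline, baseline-by-visit, treatment, visit and treatment-by-visit terms and an unstructured covariance across visits. Include everyone randomised who has any follow-up score, in the assigned arm. Apply Bonferroni across outcomes and keep the RMANOVA as a secondary analysis.

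This model still omits people with only a baseline score: about 15 of 110 under even dropout (110 − 110 × √0.75 ≈ 15). To use them as well, or to keep the multivariate gate primary, specify multiple imputation before the RMANOVA.

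Either way, report dropout by arm and visit, state the missing-at-random assumption, and add a not-at-random sensitivity analysis, for example imputation with arm-specific shifts until the conclusion changes.

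The cost is SAP wording and standard software, with no new data. There are two downsides. The multivariate gate may no longer be primary. And if dropout depends on unobserved scores differently by arm, the mixed model can be further off than the completers' contrast: in simulation at ρ = 0.5, 0.10 against 0.06 SD when one arm was affected, and 0.21 against 0.12 SD when the arms went in opposite directions. The sensitivity analysis is therefore part of the fix.

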*36-Item Short Form (SF-36; patient and caregiver health status).* The SF-36 is one of the most widely used instruments to assess self-reported Health-Related Quality of Life (HRQoL) in individuals with TBI. The items address eight dimensions of health: physical function, role-physical, bodily pain, general health, energy/vitality, social function, role-emotional, and mental health. Scores range from 0-100, with higher scores indicating better health. It has been translated Spanish, and has well-established reliability and validity in Spanish-speaking populations.

*Brief Health Literacy Screening Tool (BRIEF; caregiver health literacy).* The BRIEF is a 4-item measure of health literacy level. In its initial construction, a factor analysis indicated that the BRIEF measures one distinct construct: "health literacy" (Eigenvalue = 2.4) accounting for 60% of score variance. The BRIEF has good convergent validity with other longer measures of health literacy.

*Overall Study Timeline.* An activity and milestone timeline for the 2-year grant cycle appears in Table 1.

Table 1. Grant Cycle Timeline							
Activity	Before Start	1-4 Months	5-8 Months	9-12 Months	13-16 Months	17-20 Months	21-24 Months
IRB	█						
Guidebook Development		█					
Guidebook Piloting							
Clinician Hiring		█					
Training		█					
Enrollment			█	█	█	█	
Intervention			█	█	█	█	
Data Collection			█	█	█	█	
Data Analyses				█	█	█	
Reports					█	█	
Publications						█	

NCT00207803

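### Holm in place of Bonferroni, without the omnibus test as a precondition, would find more outcome effects at no cost in family-wise error

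*SAP*

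**What the plan says.** The SAP's analytic plan for the caregiver question specifies a Greenhouse-Geisser-adjusted repeated measures MANOVA with group, three time points, "and the treatment group by time interaction will be conducted for the set of dependent variables in Q1". The outcomes named are "health status, burden, depression, sense of coherence, quality of informal care provided, and relationship satisfaction", which makes six constructs. The decision rule for single outcomes is: "If an omnibus effect is found, follow-up Bonferroni-corrected ANOVAs will identify specific locations of effects". For the patient question, which also names six constructs, the SAP says: "The same analyses will be used for the patient dependent variables".

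Three details that the rule needs are not given:

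- **Alpha.** Neither document states a level.
- **Number of tests in the Bonferroni divisor.** Six constructs are named, but the protocol's SF-36 entry says "The items address eight dimensions of health", so the count could be larger.
- **Which effect opens the gate.** The model has a group, a time and a group-by-time effect, and the SAP does not say which of them counts as the omnibus effect.

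The protocol's power statement (Sample Estimation and Power) covers the multivariate test only. It does not mention the corrected follow-up tests.

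**The concern.** The trial asks which named outcomes the intervention changes. To claim an effect on one of them, the plan requires two hurdles in sequence: a significant multivariate test, then a p-value below the Bonferroni threshold. The second hurdle is enough for family-wise control within the question. The first adds no protection that the outcome claims need, but it can block a finding that has passed the second.

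At stake is power. With about 84 complete dyads and a medium effect, the chance of detecting an effect on a given outcome after correction is only about one in three under plausible assumptions. The stated rule gives up part of that for no needed gain in error control.

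**Working it through.** **The plan's own figure.** Enrolment is 110 dyads, "of which 55 will be in the treatment group and 55 will be in the control group". The protocol continues: "Allowing for a 25% attrition rate based on our previous data collection". 110 × (1 − 0.25) = 82.5, against the stated 84. That agrees within two dyads, so 84 / 2 = 42 per arm is used below. No alpha, family-wise error or numerical power is stated, so there is no error-rate or power figure to reproduce.

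**Direction (no simulation needed).** Take six tests at an assumed family-wise 0.05.

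- Bonferroni rejects outcome *j* if p_j ≤ 0.05/6 = 0.0083.
- The plan rejects *j* only if that holds and the omnibus test is significant. Its rejections are therefore a subset of Bonferroni's.
- Holm orders the p-values and compares them in turn with 0.05/6, 0.05/5, 0.05/4, 0.05/3, 0.05/2 and 0.05 (0.0083, 0.0100, 0.0125, 0.0167, 0.0250, 0.0500), stopping at the first failure. Any p-value at or below 0.0083 passes at every step, so Bonferroni's rejections are a subset of Holm's.
- Bonferroni and Holm each hold the family-wise error at or below 0.05 for any correlation and any pattern of true effects.

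So ungated Holm never finds less than the plan and sometimes finds more.

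**Size (simulation).** Inputs from the documents: 42 per arm, three time points, six outcomes, and a correlation between outcomes guided by the SAP's remark that "These dependent variables rarely correlate with each other higher than .60". Assumed: alpha 0.05, a 0.5 SD group difference at months 2 and 4 (the protocol says only that pilot effects were medium-sized), correlation 0.5 over time, and a group-by-time gate at 5%. The gate was run both as an averaged Wilks test and as a doubly multivariate Hotelling test. The follow-ups are Greenhouse-Geisser-adjusted group-by-time F tests.

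Power per truly affected outcome, with outcome correlation 0.3 to 0.5. The last column gives the gain in percentage points over the wider correlation range 0.3 to 0.6:

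| Outcomes affected | Plan | Holm, no gate | Gain, correlation 0.3-0.6 |
|---|---|---|---|
| One | 0.27-0.30 | 0.37-0.38 | 3 to 12 |
| Two | 0.31-0.37 | 0.37-0.40 | about 1 to 6 |
| Three | 0.36 | 0.39-0.40 | 3 to 4 |
| All six | 0.29-0.35 | 0.44-0.47 | 10 to 17 |

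If the gate is kept and only Bonferroni is changed to Holm, the gain is nil with one outcome affected, about 1 to 2 points with two or three, and 6 to 8 with all six.

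**Sensitivity.** At outcome correlation 0.5, with correlation over time of 0.3, plan against ungated Holm is 0.17-0.19 against 0.24 (one affected), 0.21-0.22 against 0.24 (two) and 0.17-0.19 against 0.29 (six). With correlation over time of 0.7 it is 0.61-0.63 against 0.66, 0.66 against 0.67, and 0.61-0.63 against 0.77. At a 0.8 SD difference the gain is 0 to 8 points with one to three affected and 7 to 10 with six.

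**Error rate (outcome correlation 0.3 to 0.6).**

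- No outcome affected: the plan makes at least one false outcome claim in 1.4% to 2.0% of trials, and ungated Holm in 3.8% to 4.6%. With 13 tests (eight SF-36 dimensions plus five other outcomes) the plan's figure is 0.8% to 1.3%.
- One outcome overwhelmingly affected: the gate is always open. The plan's error on the other five is 3.2% to 3.7% (bound 5/6 × 5% = 4.2%), and ungated Holm's is 3.8% to 4.4%.

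**The case against.** The strongest defence is that an omnibus test followed by Bonferroni is an accepted and conservative procedure. No error control fails and no two statements in the documents conflict. The multivariate test is also the one analysis that the protocol's power statement covers, so making it descriptive would change the confirmatory strategy. All of that stands. It is why the Holm substitution comes first in the fix, with removal of the gate as a preference.

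The loss also depends on the scenario. The protocol reports pilot effects on two outcomes, strain and depression, and with two or three outcomes affected the gain is small. The large figures need all six outcomes to shift equally.

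The gate itself is uncertain. With all six affected and outcome correlation 0.5, the averaged test opens more often than the Hotelling version (0.57 against 0.52). Letting a group effect open the gate too raises this to 0.73 and lifts the chance of finding at least one effect from 0.51 to 0.63. If a time effect alone can open it, the gate costs little, but it then screens nothing about treatment.

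A reader might infer that the plan uses only about a third of its 5% allowance. The documents do not support that in general. They state no 5% level. The figure (1.4/5 = 28% to 2.0/5 = 40%) applies only when no outcome is affected and the gate is a treatment-related effect. It concerns outcome claims only, since the omnibus claim takes the full level.

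A reader might also infer that the loss always grows as outcomes become more correlated. That holds when all six respond. With one or two affected, raising the correlation from 0.3 to 0.5 shrinks it: from 0.10-0.12 to 0.05-0.08 with one, and from about 0.04-0.05 to 0.02-0.03 with two.

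**Conclusion.** The point holds as a matter of efficiency. The rule is valid, and its loss of power relative to ungated Holm is certain in direction. The size is not certain: at a 0.5 SD difference and correlation 0.5 over time it runs from about 1 to 17 percentage points per affected outcome, largest when all six outcomes respond and smallest with two or three. These figures rest on an assumed alpha of 0.05, six tests and a group-by-time gate, none of which the documents state. The gate's share of the loss shrinks if a group or time effect can also open it.

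It should not be read as a failure of error control or as a flaw that invalidates the analysis. It is a cheap improvement. It concerns each question separately and does not address error across the caregiver and patient families together.

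**What to change.** **Minimum change.** In the SAP's decision rule, replace Bonferroni-corrected with Holm-corrected, and say what is tested: the group-by-time effect on each of the six outcomes, at a family-wise 0.05 within each question. If the SF-36 contributes more than one score, state the larger number of tests.

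**Preferred change.** Also report the multivariate test alongside the outcome tests without making it a condition for them. Suggested wording: *The group-by-time effect on each of the six outcomes will be tested with Holm's step-down procedure at a family-wise 0.05 within each question (caregiver, patient). The multivariate test will be reported alongside and is not a condition for the outcome tests.* If the sponsor keeps the gate, the SAP should state its alpha and which effect opens it.

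**Cost.** A sentence or two of SAP text and no new data. Dropping the gate is a larger change of strategy than the Holm substitution and deserves a deliberate decision. Holm has no simple matching set of simultaneous confidence intervals, so intervals would be reported unadjusted or Bonferroni-adjusted. The change must be fixed before outcome results are seen.
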